Eligible patients will receive standard treatment of 12(+/-1) weeks of rigid hard collar immobilization, as well as an 8-week course of PTH analog during this time. Drug will be initiated as soon after the injury as possible, and at the latest 4 weeks from injury which will allow for completion of 8 weeks of drug administration during the period of hard collar immobilization. Teaching on drug administration will be provided for enrolled patients and their caregiver, if applicable, by designated study personnel prior to drug initiation – either while inpatient, or at the outpatient endocrinology clinic visit. Treatment subjects will otherwise receive the routine care that was provided to historical controls in terms of length of hard collar immobilization spine fracture clinic follow-up and radiographic evaluation. Treatment subjects will be followed with weekly phone calls (see Table 1) by clinical personnel on the study team for the duration of the 8-week treatment.

Study participants will be followed at the spine fracture clinic according to our usual protocol every 4 weeks +/- 1 week (from the date of injury) out to 12 weeks. All patients will fill out VAS Neck and Neck Disability Index (NDI) physical function questionnaires at each clinic visit. Use of narcotic pain medication will be collected at each clinic visit under routine care.

DEXA scans will be obtained for all participants to assess baseline bone density. If a patient has had a DEXA scan for routine care within the 12 months prior to consent, that scan will be used as the baseline test and a separate test for research will not be ordered. If needed, baseline DEXA will need to be completed after consent and by time of the 12 week visit.

All radiographs for treatment subjects will be obtained as part of routine care. These include AP/Lateral at each of the 4 (+/-1) week and 8 (+/-1) week clinic visits, and Flex/Ext at the 12 (+/-1) week clinic visits. Final (12 +/-1 week) flexion/extension radiographs will be evaluated for translational motion at the fracture site measured at the posterior cortex of the dens and evaluated by the following criteria: None, Minimal (<2 mm), Moderate (2-4 mm), Mobile (>4 mm).

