A non-contrast cervical spine CT scan at will be obtained for research purposes at UVMMC at the 12 (+/-1) week time point. Final fracture characteristics (angulation, displacement) will be documented based on the 12-week CT scan. Amount of fracture healing will be assessed on CT by a radiologist by the following method¹⁰: 1 mm coronal and sagittal sections across the fracture will be individually analyzed. The radiologist will reconstruct the CT scan to true orthogonal coronal and sagittal images. Each slice will be analyzed for the width of bridging bone as a percentage of the width of the fracture line. The sum total of the widths of bridging bone, divided by the sum total of the fracture widths will be expressed as a percentage of total healing for that patient. This absolute % of bridging bone will be the primary outcome¹⁰. Fracture characteristics (obliquity, angulation, displacement, comminution) on the injury CT scan will be documented for later post-hoc analysis. Additionally, we will also compare our study group results to the union rates documented in the existing literature.

Control subjects:

Our historical control group will be comprised of patients with type II odontoid fractures (defined above) who were previously treated in our spine fracture clinic. Patients will have been injured within the past ten years, and have completed 12 +/-1 weeks of hard collar immobilization. Potentially eligible historical controls will be identified by database query and chart/radiographs review of patients from the fracture clinic. A request will be made of the UVMMC Data Management Office to identify potential control subjects. Identified potential control patients will be approached as outlined under 'Consent Process', below.

If patients are interested in active study participation by coming in for a study visit (research imaging: *Control cohort A: Active control participants*), written informed consent will be obtained in person at UVMMC by designated research personnel. Consented active control subjects will then complete a CT scan of the cervical spine for comparison to those from our study group. If flexion-extension cervical XR were not obtained 11 or more weeks after initiation of hard collar treatment as part of their routine care, flexion-extension cervical XR will be obtained for the study. Additionally, these control subjects will complete VAS Neck and NDI physical function questionnaires.

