Statistical Considerations: Delineate the precise outcomes to be measured and analyzed. Describe how these results will be measured and statistically analyzed. Delineate methods used to estimate the required number of subjects. Describe power calculations if the study involves comparisons. Perform this analysis on each of the primary and secondary objectives, if possible.

Primary outcome will be % bridging bone on CT scan at 12 weeks as described previously based on 1 mm sagittal and coronal cuts. The study radiologist evaluating the primary outcome will be blinded to patient group (treatment vs. historical control). Secondary outcomes will include VAS Neck and NDI scores, and motion on flexion/extension radiographs.

Assuming 60% nonunion rate in our historical control group and 20% in our study group, with alpha = 0.05 and 80% power, we would need to enroll 44 patients in a randomized trial (22 control, 22 study patients) to show a statistical difference. This study is intended as an initial pilot study to suggest efficacy, and further inform a future randomized controlled trial. We see 15-20 new type II dens fractures treated non-operatively per year in our fracture clinic, and estimate the initial pilot of 10 treatment patients + 12 control subjects can be completed within 2 years.

Data analysis will be based on multi-variate regression using ANOVA, with $p < 0.05$ recognized as a significant difference. Plan is for as treated analysis; if there are patients who receive only partial course of study drug for any reason, they will be evaluated descriptively as a separate group. Additionally, we will also compare our study group results to the union rates documented in the existing literature.

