Under routine care, patients with dens fractures are monitored for any fracture displacement using x-rays or neurologic changes that require a change in treatment plan. Study participants will be monitored in the same way. For treatment subjects: if the fracture clinic physician [name] has any concerns for abnormal fracture displacement or new neurologic deficit, the PI (or another fellowship-trained orthopaedic or neurologic spine surgeon on the study team as delegated by the PI) will review all radiographic evidence of fracture displacement or neurologic deficit. Based on fracture displacement and neurologic changes, the patient may require a change in their treatment plan. Study patients are treated no differently from non-study patients in this regard. If there is a significant change in their treatment plan (e.g. surgery), these patients will be withdrawn from the study at the discretion of the PI.

All study participants may voluntarily withdraw themselves from the study at any time. If a participant decides to withdraw, the study will continue to use the information already collected for the study before withdrawal. This is noted in the informed consent forms for both control and treatment subjects.

If a patient were withdrawn from the study for any reason, the standard of care treatment for their fracture would resume.

Sources of Materials: Identify sources of research material obtained from individually identifiable human subjects in the form of specimens, records or data. Indicate whether the material or data will be obtained specifically for research purposes or whether use will be made of existing specimens, records or data.

Sources of research information will be provided in the electronic health records (including imaging) and study questionnaires. This information will be used for eligibility screening, safety monitoring, primary outcome (CT scans) and secondary outcome (radiographs, VAS and NDI) measures. Material will be derived from both existing sources in the electronic health record and research-driven procedures. Together these materials include:

For treatment subjects

- Lab results and office notes
- Office notes from clinical exams and consultations, including VAS Neck and NDI measures
- Radiographs and CT scans
- Drug diary

For historical comparison subjects (Control cohort A: active control participants)

- Lab results and office notes
- Study questionnaires (VAS Neck and NDI)
- Radiographs and CT scans

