Historical Comparison Subjects

Inclusion Criteria (all must be yes)

1. Age 50 years or older at time of fracture
2. Anderson and D'Alonzo type II dens fracture identified on cervical spine CT, with or without a C1 ring injury. Type II dens fractures are defined as involving the area of the dens between the inferior aspect of the anterior C1 ring and not extending into the superior articular facets of C2.
3. Fracture injury occurred within 10 years before consent
4. The patient completed 12 (+/- 1) weeks of hard collar immobilization

Exclusion Criteria (all must be no)

5. Any history of prior teriparatide or abaloperatide use
6. Use of denosumab in the past year

Inclusion of Minorities and Women: Describe efforts to include minorities and women. If either minorities or women are excluded, include a justification for the exclusion.

Women will be included in the study whenever the eligibility criteria are met. Every effort will be made to recruit minorities. Recruitment efforts will not differ by sex or by ethnicity.

Inclusion of Children: Describe efforts to include children. Inclusion is required unless a clear and compelling rationale shows that inclusion is inappropriate with respect to the health of the subjects or that inclusion is inappropriate for the purpose of the study. If children are included, the description of the plan should include a rationale for selecting or excluding a specific age range of children. When included, the plan must also describe the expertise of the investigative team in working with children, the appropriateness of the available facilities to accommodate children, and the inclusion of a sufficient number of children to contribute to a meaningful analysis relative to the purpose of the study. Provide target accrual for this population. Identify whether children are wards of the state. **If children are excluded** then provide appropriate justification.

The fracture of interest occurs very rarely in minor subjects, and the safety and effectiveness of the study drug has not been established in pediatric patients. Children will not be included in this study.

For protocols including the use of an investigational drug, indicate whether women of childbearing potential have been included and, if not, include appropriate justification.

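### Blinding is stated only for the primary CT read; the fracture-motion outcome has no named or masked reader, and its lowest band has no millimetre limit

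*Combined protocol and SAP*

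**What the plan says.** Under Statistical Considerations, blinding is given in one sentence: "The study radiologist evaluating the primary outcome will be blinded to patient group (treatment vs. historical control"). The sentence after it reads: "Secondary outcomes will include VAS Neck and NDI scores, and motion on flexion/extension radiographs". It adds nothing on masking, and no other section mentions blinding.

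The motion method is under Study Design, Treatment subjects. The final "flexion/extension radiographs will be evaluated for translational motion at the fracture site measured at the posterior cortex of the dens" and are then "evaluated by the following criteria: None, Minimal (<2 mm), Moderate (2-4 mm), Mobile (>4 mm"). No reader, repeat reading or agreement check is given. By contrast, the same section assigns the CT read to a radiologist and describes it slice by slice. The bands are not restated under Control subjects. The text below Table 1 confirms that these films serve the secondary motion outcome.

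The films differ in origin. For the treated group, "All radiographs for treatment subjects will be obtained as part of routine care", with flexion/extension views at 12 (+/-1) weeks. For active controls (cohort A), a research film is taken "If flexion-extension cervical XR were not obtained 11 or more weeks after initiation of hard collar treatment as part of their routine care". Review-only controls (cohort B) contribute what the medical record holds. The control criterion on injury date is "Fracture injury occurred within 10 years before consent".

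**The concern.** Translation at the posterior cortex is read off a film by a person, so the result depends on that reader. The drug is given openly and the comparator is historical. Of the three secondary outcomes, the pain and disability scores come from patients who know their treatment. Motion is the one that could readily be masked at reading, and the plan does not provide for it.

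The band definition adds a second opening. The 2 mm and 4 mm cuts are explicit, but nothing separates *None* from *Minimal*. That boundary divides no motion from some motion, which is the contrast most easily read as stability. A reader who knows the group has discretion exactly there. The pilot is meant to inform a later randomized trial, so a loosely defined measure could be carried forward.

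**Working it through.** **The plan's own figure.** No power or sample-size figure is given for motion. The one figure, 44 patients (22 per group), concerns nonunion at 60% versus 20%, with alpha 0.05 (taken as two-sided) and 80% power. The arcsine formula reproduces it:

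- h = 2·asin(√0.6) − 2·asin(√0.2) = 1.772 − 0.927 = 0.845
- n = 2·((1.960 + 0.842)/0.845)² ≈ 22 per group

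It has no bearing on the motion outcome.

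**Blinding, outcome by outcome.**

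| Outcome | Reader named | Masking stated |
|---|---|---|
| CT bridging bone (primary) | Study radiologist | Yes |
| Motion (secondary) | None | None |
| VAS Neck, NDI (secondary) | Patient-reported | Not applicable |

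**Bands.** A reading of 0 mm or 0.4 mm satisfies *Minimal* (<2 mm). Each could also be called *None*, because no limit excludes it. The overlap is at this edge only.

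**Film dates.** Treated films fall at 12 ± 1 weeks, that is 11 to 13 weeks after injury. Control films may date from any time from 11 weeks after the collar was started, with no upper limit, or be new study films after an injury up to 10 years (about 520 weeks) before consent. A date well beyond 13 weeks after injury therefore identifies a control.

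**Illustration at the *None* boundary.** All inputs are assumptions. Let the true share with any motion be the same in both groups, b = 30% or 50%. Let a reader aware of the group move a fraction m = 20% or 40% of treated patients with motion into *None*. The false difference is b·m. The last two columns give the two-sided Fisher rejection rate at the 0.05 level with 12 controls and 10 treated patients.

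| b | m | False difference | Rejection rate, m = 0 | Rejection rate, with shift |
|---|---|---|---|---|
| 30% | 20% | 6 points | 2.6% | 3.3% |
| 30% | 40% | 12 points | 2.6% | 5.4% |
| 50% | 20% | 10 points | 3.2% | 5.3% |
| 50% | 40% | 20 points | 3.2% | 12.1% |

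**Check at the 2 mm and 4 mm cuts.** Suppose united fractures move less than 2 mm and nonunions spread evenly over 0 to 6 mm (both assumptions). A downward reading shift d carries a share 2d/6 of nonunions across a cut. With 10 treated patients at the planned 20% nonunion rate:

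- d = 0.5 mm: 10 × 0.20 × 1.0/6 = 0.3 patients
- d = 1.0 mm: 10 × 0.20 × 2.0/6 = 0.7 patients

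At the 60% rate assumed for controls the results would be 1.0 and 2.0. The explicit cuts thus leave little room for reclassification in the treated group.

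**The case against.** The strongest reply is that this is a reporting gap in an unpowered secondary outcome of a pilot whose primary read is already blinded. That stands as a limit on importance. It is not a reason to leave the gap, since the remedy needs no one new.

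Three stronger readings are tempting, and the documents do not support them.

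- **That the treating team grades motion.** Withdrawal Procedures says that the PI or a delegate "will review all radiographic evidence of fracture displacement or neurologic deficit". That review happens only when the clinic physician is concerned about displacement or a new deficit, and it serves decisions on the treatment plan. It says nothing about grading the outcome. An unblinded read is possible but not stated.
- **That the millimetre value is thrown away.** Translation is described as measured and then classed, and the outcome is named simply as motion. No passage says whether the value is kept or analysed.
- **That a large share of treated patients would be misclassified at 2 or 4 mm.** Spreading every patient's translation evenly over 0 to 6 mm, with d of 0.5 to 1.0 mm, gives 10 × 2d/6 = 1.7 to 3.3 of 10 patients. But that spread puts 4/6 = 67% of treated patients at 2 mm or more, which sits badly with the 20% nonunion the plan expects in that group.

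It is also fair to say that analysing millimetres does not remove observer bias, because a systematic shift of 0.5 to 1 mm would move a mean by the same amount. Masking is the remedy, and the millimetre value only makes the result more transparent.

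**Conclusion.** The point holds in a limited form and is worth correcting. Blinding is stated for the primary CT read only. Motion has neither a named reader nor stated masking, and its two lowest bands overlap. With an open-label historical comparison and film dates that can give away the group, the outcome is exposed to observer bias. The primary analysis and the sample size are untouched.

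The size of the bias cannot be derived from the documents. The 6 to 20 point illustration rests entirely on assumed values for true motion and reader behaviour, and the plan does not specify a Fisher test for motion. It shows that discretion at the *None* boundary can matter with 22 patients; it does not show that bias will occur.

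**What to change.** Extend the blinding sentence in Statistical Considerations in three respects:

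- **Reader and masking.** The same blinded study radiologist measures translation on all available treated and control flexion/extension films, de-identified, with group and dates removed, both groups mixed in random order.
- **Recording.** The millimetre value is recorded and reported beside the bands, using the same method for controls.
- **Lowest band.** Either give *None* a millimetre limit tied to measurement error, or report it together with <2 mm.

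The cost is a few lines of protocol text and modest reading time for at most about 10 + 12 = 22 film pairs, fewer if some cohort B controls have no such films. No new reader or imaging is needed. Removing dates masks the reader only; it does not make the groups alike in time since injury, which should be acknowledged when motion is reported.

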No. However, the proposal involves use as an experimental treatment of a fracture that is most common in elderly patients with osteoporosis, and the study drug is approved for the treatment of individuals with osteoporosis who are at high risk for these fractures.

SUBJECT CHARACTERISTICS, IDENTIFICATION AND RECRUITMENT

Subject Selection: Provide rationale for subject selection in terms of the scientific objectives and proposed study design.

The study population includes patients greater than or equal to the age of 50. This is the population that sustains dens fractures most frequently.

Vulnerable Populations: Explain the rationale for involvement of subjects (e.g., cognitively impaired, Non-English speaking, prisoners, students). Discuss what procedures or practices will be used in the protocol to minimize their susceptibility to undue influences and unnecessary risk (physical, psychological, etc.).

Not applicable

Inclusion/Exclusion Criteria: Eligibility and ineligibility criteria should be specific. Describe how eligibility will be determined and by whom. Changes to the eligibility criteria at a later phase of the research have the potential to invalidate the research.

Treatment Subjects

Inclusion Criteria (all must be yes)

1. Age 50 years or older at time of consent
2. Anderson and D'Alonzo type II dens fracture identified on cervical spine CT, with or without a C1 ring injury. Type II dens fractures are defined as involving the area of the dens between the inferior aspect of the anterior C1 ring and not extending into the superior articular facets of C2.
3. Fracture is deemed amenable to non-operative treatment by treating fellowship trained spine surgeon
4. Fracture occurred within the 3 weeks before consent
5. Report of ≥ 12 months of amenorrhea within the last year if the patient is female

Exclusion Criteria (all must be no)

6. Personal history of radiation therapy to the skeleton
7. Personal history of osteosarcoma
8. Personal history of Paget's disease
9. Personal history of bone metastases or skeletal malignancy
10. Hereditary disorders predisposing to osteosarcoma
11. Prior teriparatide or abaloperatide use
12. Use of denosumab within the past year
13. Psychological impairment that precludes following hard collar immobilization recommendations
14. Ineligible based on history of active or recurrent kidney stones, CMP, PTH, Phos results to be determined on a case-by-case basis by an endocrinologist on the study team

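### Controls must have completed about 11 to 13 weeks of collar wear but treated patients need not; if past collars were extended because of non-healing, this one-sided condition could attenuate a drug effect

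*Combined protocol and SAP*

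**What the plan says.** **Controls.** Study Design, Control subjects, requires that they "have completed 12 +/-1 weeks of hard collar immobilization". Inclusion/Exclusion Criteria, Historical Comparison Subjects, criterion 4 repeats it: "The patient completed 12 (+/- 1) weeks of hard collar immobilization". Every inclusion criterion in that list must be met.

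**Treated patients.** The same duration appears as planned care: "Eligible patients will receive standard treatment of 12(+/-1) weeks of rigid hard collar immobilization". It is not among their eligibility criteria. The nearest entry condition is a judgement made at the start: "Fracture is deemed amenable to non-operative treatment by treating fellowship trained spine surgeon".

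**Timing of the outcome in treated patients.** The endpoint CT "will be obtained for research purposes at UVMMC at the 12 (+/-1) week time point". Motion is read at the same visit: "Final (12 +/-1 week) flexion/extension radiographs will be evaluated for translational motion at the fracture site".

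**Leaving the treated comparison.** Withdrawal Procedures says: "If there is a significant change in their treatment plan (e.g. surgery), these patients will be withdrawn from the study", at the investigator's discretion. Longer collar wear is not named. Statistical Considerations says: "Plan is for as treated analysis; if there are patients who receive only partial course of study drug for any reason", those patients are described separately. Nothing is said about collar duration.

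**The concern.** Whether a control meets criterion 4 is known only about three months after injury, when the state of healing is also becoming known. The condition therefore selects controls on something that happens after baseline and may depend on the outcome. No matching condition applies to treated patients.

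Take two patients whose fractures still move on the week-12 films and whose collars are continued. The treated one has already had the endpoint CT and counts. The control has gone past 13 weeks and, on the natural reading, is ineligible. If such patients exist, the collar-alone group loses poor healers and the treated group does not. Control bridging bone would be too high, control motion too low, and the comparison tilted against the drug. The pilot is meant to inform a randomized trial, so a distorted control rate would also carry into that trial's planning.

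**Working it through.** **Inputs.** From Statistical Considerations: non-union 60% in controls and 20% in treated patients, alpha 0.05, power 80%, 22 + 22 patients for a randomized trial, and 12 controls + 10 treated in the pilot. The share f of non-united controls lost because the collar stayed on past week 13 is not in the documents; 10% to 50% is assumed.

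**The plan's own figure.** Two-sided test of two proportions, pooled variance, no continuity correction (sidedness is not stated):

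n per arm = [1.96·√(2 × 0.4 × 0.6) + 0.842·√(0.24 + 0.16)]² / 0.4² = 22.3

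Rounded up this is 23 per arm (46 in total), against the stated 22 (44). Power at 22 per arm is 79.4%, so the stated size is reproduced closely enough.

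**Effect of one-sided exclusion.** Assume that 60% is the rate before the exclusion, that no united control is lost, and that all treated patients stay. Then:

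control non-union = 0.6(1 − f) / [0.6(1 − f) + 0.4]

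- f = 10%: 0.54 / 0.94 = 57.4%
- f = 25%: 0.45 / 0.85 = 52.9%
- f = 50%: 0.30 / 0.70 = 42.9%

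| f | Control non-union | Difference from 20% | Power, 22 + 22 | Power, 12 + 10 |
|---|---|---|---|---|
| 0 | 60.0% | 40.0 points | 79.4% | 47.1% |
| 10% | 57.4% | 37.4 points | 73.9% | 42.2% |
| 25% | 52.9% | 32.9 points | 62.9% | 34.2% |
| 50% | 42.9% | 22.9 points | 36.8% | 19.4% |

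Power uses the same normal approximation.

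**When the assumed effect would vanish.** Setting 0.6(1 − f) = 0.2(1 − 0.6f) gives 0.4 = 0.48f, so f = 83%.

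**If the drug did nothing** (60% in both groups), f = 25% would make it look 60 − 52.9 = 7.1 points worse than collar alone.

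**Offset from the lower limit.** The window also drops controls whose collar came off before week 11, some perhaps because they had healed. Losing 10% of united and 25% of non-united controls gives 0.45 / (0.45 + 0.36) = 55.6%, a difference of 35.6 points. Equal losses from both groups leave the 40 points unchanged. Table 1 schedules no flexion/extension film before week 12, so early removal for demonstrated stability seems less likely than extension after it, but the documents do not settle this.

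**Scale.** These are non-union rates. The primary outcome is percentage bridging bone, for which the plan gives no mean or standard deviation. The direction would be the same; the size on that scale cannot be computed.

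**The case against.** **The mechanism is not documented.** Routine care is described as a fixed course with final films at about week 12. The stated triggers for changing treatment are displacement and neurologic change, with surgery as the example. Nothing says collars were continued for non-union, so f could be near zero. This stands, and it is why the bias is conditional.

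**The upper limit may not be meant.** The plus-or-minus notation is also the protocol's label for the final visit, and a patient who wore the collar for 16 weeks did complete a 12-week course. That reading is possible. However, the same section writes an open minimum of 11 weeks when it wants one, for the control flexion/extension films, and under an at-least reading the upper tolerance does nothing. A chart reviewer would probably exclude the 16-week patient, so the wording needs changing either way.

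**The 60% may already be post-selection.** Statistical Considerations states it for the historical control group, which is defined by the completed-collar condition. If so, applying f to it counts the exclusion twice. This stands, so the shrunken differences are illustrations and not corrections to the plan's effect.

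**The shift is small against pilot noise.** With 12 and 10 patients the standard error of a 60% versus 20% difference is √(0.24/12 + 0.16/10) = 19 points, against shifts of about 3 points at f = 10% and 7 at f = 25%. This is true, but a bias is not excused by imprecision when removing it costs little.

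**A reader might infer that the criterion hides a drug effect, or that it demonstrably removes non-unions.** The documents support neither. No frequency of extended wear is given, and cancelling the assumed effect would take f of about 83%.

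**Conclusion.** The asymmetry is in the text: controls are selected on a completed collar duration, and treated patients are not. That it biases the comparison is conditional on past collars having been extended beyond week 13 for non-healing. If they were, control healing would look better than it was and a drug effect could be attenuated. On the stated assumptions this costs roughly 3 to 17 points of the planned 40 for f between 10% and 50%, less whatever the early-removal exclusion gives back.

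This criterion does not fix the net bias of the whole design. Active controls may be scanned up to ten years after injury and can show union gained after week 12, which is a separate problem. The point merits a change because selection on a post-baseline condition in one group only is avoidable, not because the size of the bias is known.

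**What to change.** In Study Design, Control subjects, and in criterion 4 for Historical Comparison Subjects, replace the completed-duration condition with the baseline rule used for treated patients: hard collar chosen as the initial non-operative treatment. This changes which past patients count as controls, not anyone's care. Merely lifting the upper limit to at least 11 weeks would be weaker, because controls alone would still be selected on post-baseline collar time.

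Also:

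- Record the collar stop date and the reason for stopping or continuing in both groups.
- Report how many in each group fell below 11 or above 13 weeks. This shows how many controls the present window would have excluded.
- State how a later change to surgery is handled, in the same way for controls and treated patients.
- Give the 11-to-13-week subset as a sensitivity analysis.

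The cost is one amended criterion in two places and a few fields in a chart review already planned. The downside is more variable collar exposure among controls, which the recorded dates make visible. The change does not resolve control CTs taken well after week 12: a readmitted control who united later would still be read as united.
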